3.2.2 SARS-CoV-2 Antibody Assay

3.2.2.1 Qualitative baseline assessment

Participants will have blood draws on day 1 (before vaccination) as noted in 3.2.1. Serum will be assayed for the presence of SARS-CoV-2 antibody using the AdviseDx SARS-CoV-2 IgG II assay and the Alinity I SARS-CoV-2 IgG assay. The assays are intended for use as an aid in identifying individuals with an adaptive immune response to SARS-CoV-2 indicating recent or prior infection. Serologic testing will be completed in periodic batches throughout the course of the study and will therefore not be available in real-time or for use in clinical decision-making. The current tests described above are allowed under the FDA's Emergency Use Authorization during the COVID-19 pandemic. Duke will share participant results with each study site as permitted by FDA and CDC. Study sites may share results with participant as permitted by FDA, CDC, and local site regulations.

3.2.2.2 Quantitative SARS-CoV-2 assessments

Participants will have blood draws on Day 1 (before vaccination) and following each vaccination according to schedules outlined in Section 5.1 to be stored for serum COVID-19 neutralization assays. COVID-19 neutralizing antibody titers will be compared between groups receiving COVID-19 and IIV4 simultaneously or sequentially for each variant tested. Participants will not receive individual COVID-19 antibody titer results; these are not routinely used in clinical practice.

3.2.3 Future studies

In addition to the specified analyses described thus far, there may be other tests or assays that have yet to be identified that may be important for interpreting our study findings or of relevance to vaccine outcomes. Additional laboratory assays may test for antibodies against other bacteria or viruses, markers of inflammation, or used in research on the health of the participants. Specimens banked for use in other studies will be linked to information (including identifying information) that participants provided to the study. Subjects/subject's legally authorized representative (LAR) must agree to potential future use of samples in order to be in the study. Because it is unknown if future testing will be of any utility, results of future testing will not be provided.

4 STUDY ENROLLMENT AND WITHDRAWAL

4.1 Subject Inclusion Criteria

Subjects who meet all of the following criteria will be eligible to participate in this interventional study.

1. Persons aged ≥ 5 years if receiving primary two-dose mRNA COVID-19 vaccine series or persons aged ≥ 12 years if receiving a booster mRNA COVID-19 vaccine dose according to FDA authorization or approval and ACIP recommendation. Note: receipt of an mRNA COVID-19 vaccine within 8 hours of enrollment is permitted
* Individuals age 5-11 receiving a booster may be enrolled in the event a booster for individuals age 5-11 is authorized or approved and recommended by the ACIP.
2. English or Spanish literate
3. Intention of receiving influenza vaccine and mRNA COVID-19 vaccine based on ACIP-CDC guidelines
4. Willing to provide written informed consent
5. Intention of being available for entire study period and complete all relevant study procedures, including follow-up phone calls and clinic visits

4.2 Subject Exclusion Criteria

Subjects who meet any of the following criteria will not be eligible to participate in this study:

1. Currently pregnant, planning to become pregnant within the first three months of the study per participant self-report or likely to be pregnant per screening criteria as defined in Section 5.1 at Visit 1
2. Prior receipt of IIV4 during the respective influenza season in which they are being enrolled
3. < 9 years of age and recommended to receive two doses of IIV4 during the respective influenza season in which they are being enrolled
4. Prior receipt of non-mRNA COVID-19 vaccine
5. Documented COVID-19 infection within 6 weeks prior to enrollment confirmed by either medical history or lab testing
6. History of severe allergic reaction after a previous dose of any influenza vaccine; or to an influenza vaccine component, including egg protein
7. History of severe adverse reaction associated with a vaccine and/or severe allergic reaction (e.g. anaphylaxis) to any component of an mRNA vaccine
8. Receipt of any licensed inactivated vaccine within 2 weeks prior to enrollment in this study, receipt of any licensed live vaccine within 4 weeks prior to enrollment in this study, or receipt of Shingrix (Zoster Vaccine Recombinant, Adjuvanted) or HEPLISAV-B (Hepatitis B Vaccine (Recombinant), Adjuvanted) vaccine within 6 weeks prior to enrollment in this study or planning receipt of any vaccines following enrollment until 6 weeks after receipt of the second dose of mRNA COVID-19 vaccine
9. Has an active neoplastic disease (excluding non-melanoma skin cancer or prostate cancer that is stable in the absence of therapy) or a history of any hematologic malignancy*

**Participants with a history of malignancy may be included if, after previous treatment by surgical excision, chemotherapy or radiation therapy, the participant has been observed for a period that in the investigator's estimation provides a reasonable assurance of sustained cure*

10. Thrombocytopenia, bleeding disorder, or anticoagulant use contraindicating intramuscular injection (a daily aspirin may be acceptable).
11. Has immunosuppression as a result of an underlying illness or medications, such as antirejection/transplant regimens or immunomodulatory agents. Stable HIV disease is permitted per the following parameters:
 - a. Confirmed stable HIV disease defined as document viral load <50 copies/mL and CD4 count >200 within 6 months before enrollment, and on stable antiretroviral therapy for at least 6 months
12. Has known hepatitis B (HBV) or hepatitis C (HBC). Stable HBV or HBC are permitted per the following parameters:
 - a. If known HBV: confirmed inactive chronic HBV infection: HBsAg present for ≥ 6 months and HBeAg negative, anti-HBe positive; serum HBV DNA <2000 IU/mL; persistently normal ALT or AST levels; in those who had liver biopsy, findings that confirm absence of significant necroinflammation
 - b. If known HCV: evidence of sustained virological response for ≥ 12 weeks after treatment or without evidence of HCV RNA viremia (undetectable HCV RNA)
13. Use of oral, parenteral, or high-dose inhaled glucocorticoids*
**For definition of high-dose inhaled glucocorticoids, reference Appendix B.*
14. History of Guillain-Barré syndrome
15. Prior enrollment in this study during the 2021-22 flu season
16. Anyone who is already enrolled or plans to enroll in another clinical trial with an investigational product during the study period.*
**Per protocol, co-enrollment in observational or behavioral intervention studies are permitted at any time. An investigational product may be permitted for therapy of an illness condition that occurs during the study period e.g. COVID-19 illness.*
17. Hearing loss determined by the investigators to prevent successful communication over the phone
18. History of myocarditis or pericarditis
19. History of multisystem inflammatory syndrome in children (MIS-C) or adults (MIS-A).
20. Has injury or other reason why deltoid site on both arms cannot be used for vaccinations.
21. Any condition which, in the opinion of the investigators, may pose a health risk to the subject or interfere with the evaluation of the study objectives.
22. Anyone who is a relative of any research study personnel.
23. Anyone who is an employee of any research study personnel.

4.3 Temporary Delay Criteria (Visit 1, 2 and 3 (for primary COVID-19 vaccine series))

1. History of febrile illness ($> 100.0^{\circ}\text{F}$ or 37.8°C) within the past 72 hours prior to vaccine administration

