Description of Study Procedures:	
This study is a prospective, randomized clinical trial. During this study, participants will be randomly assigned to receive quadrivalent inactivated influenza vaccine (IIV4) and mRNA COVID-19 vaccine either simultaneously or sequentially, 7-14 days apart. For participants receiving their primary dose series, a second dose of mRNA COVID-19 vaccine will be administered either 3 to 8 weeks or 4 to 8 weeks following the first dose, depending upon the mRNA COVID-19 vaccine provided. Participants receiving a booster dose of mRNA COVID-19 vaccine will receive a single COVID-19 dose within the study per current CDC guidelines.
 
Solicited symptoms of reactogenicity will be assessed on vaccination day and daily during the 7 days following each Vaccination Visit using either electronic or paper symptoms diaries, depending on study participant preference. Quality of life data will be collected using electronic or paper diaries on day of Vaccination Visit 1 and daily during the 7 days following the visit. Serious adverse events and adverse events of special interest will be collected throughout the duration of the study.

	
Serum samples from participants will be collected for determination of COVID-19 serostatus at baseline. Serum samples will be taken throughout the study to determine IIV4 immunogenicity and for potential future studies.

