On August 12, 2021, the FDA amended the Pfizer-BioNTech and Moderna mRNA COVID-19 vaccine EUAs to include the use of a third dose of vaccine in specific immunocompromised populations for persons 12 years of age and older and persons 18 years of age or older for the respective vaccines.¹⁹ Additionally, the CDC also recommended that moderate or severely immune compromised populations receive an additional third dose of the mRNA COVID-19 vaccines to enhance the immune response²⁰. Subsequent to these actions, the U.S. government has expanded authorizations and recommendations for a third dose of COVID-19 vaccine as infections rose from the coronavirus Delta variant and then the Omicron variant, citing data indicating diminishing protection from the vaccines over time. The FDA initially authorized a booster dose for both Pfizer-BioNTech and Moderna mRNA COVID-19 vaccines for all persons 18 years of age and older on November 19, 2021. Subsequent to this action, the EUA was extended for the Pfizer-BioNTech mRNA COVID-19 vaccine to include 16-17 year olds on December 9, 2021 and 12-15 year olds on January 3, 2022. The CDC has made comparable recommendations to follow the EUAs²¹⁻²⁴. Both the EUA and recommendations for the interval between the primary series and booster dose have also been shortened to 5 months. On March 29, 2022 FDA authorized a second booster dose for persons aged 50 and older and certain immunocompromised individuals; CDC updated guidance for second booster doses, with a 4-month interval between a first and second booster dose^{13,17}.

Local and systemic side effects occurring within the week after vaccination as reported from the BNT162b2 Phase2/3 reactogenicity subset are noted in Table 1. In general, both local and systemic side effects were reported more frequently in those who were younger and following the second dose of vaccine.

Table 1. BNT162b2 Reactogenicity (Phase 2/3)²⁵

	Dose 1		Dose 2	
	16-55 years	>55 years	16-55 years	>55 years
Local				
Pain	83.1%	71.1%	77.8%	66.1%
Redness	4.5%	4.7%	5.9%	7.2%
Swelling	5.8%	6.5%	6.3%	7.5%
Systemic				
Fever	3.7%	1.4%	15.8%	10.9%
Fatigue	47.4%	34.1%	59.4%	50.5%
Headache	41.9%	25.2%	51.7%	39.0%

Chills	14.0%	6.3%	35.1%	22.7%
Vomiting	1.2%	0.5%	1.9%	0.7%
Diarrhea	11.1%	8.2%	10.4%	8.3%
Muscle pain	21.3%	13.9%	37.3%	28.7%
Joint pain	11.0%	8.6%	21.9%	18.9%

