The current protocol allows for inclusion of persons receiving a booster dose of mRNA COVID-19 vaccine. Administration of booster dose mRNA COVID-19 vaccines to participants who are enrolled in this protocol, will adhere to current FDA prescribing recommendations for licensed or EUA mRNA COVID-19 vaccines and to ACIP recommendations for their use as the approvals and recommendations are made. Inclusion of persons receiving a booster dose of COVID-19 vaccine will allow for enhanced recruitment during the influenza vaccination season in which it is expected that most adults and many children receiving an mRNA COVID-19 vaccine in this study will be receiving a booster dose rather than an initial vaccine two-dose series.

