3 STUDY DESIGN

3.1 Main study design

This study is a prospective, randomized, clinical trial to assess the safety of simultaneous versus sequential administration of mRNA COVID-19 and IIV4 vaccines in 450 persons age ≥ 5 years enrolled at Duke University Medical Center (Lead Contractor), Johns Hopkins University (Contributing Contractor), and Cincinnati Children's Hospital Medical Center (Contributing Contractor). Participants will be enrolled in the 2021-2022 and 2022-2023 influenza seasons. Individuals will be enrolled who have not received their influenza vaccine during the influenza season during which they are recruited and are either receiving a booster dose of mRNA COVID-19 vaccine (for ages booster is authorized and recommended) or are receiving a primary two-dose mRNA COVID-19 vaccine series (5 years of age or older). Future mRNA COVID vaccines may include SARS-CoV-2 viral variants which may be included in this study if authorized or approved by the FDA and recommended by the CDC. Health, demographic and health-related quality of life (HRQOL) data will be collected from study participants 12 years of age or older at baseline. All participants receiving an mRNA COVID-19 vaccine on Day 1 (Visit 1) will be randomized to receive quadrivalent inactivated influenza vaccine (IIV4) or placebo. Persons aged < 65 years will receive standard dose IIV4 (SD-IIV4) or saline placebo injection. To qualify for the study, children < 9 years of age must only need to receive a single dose of IIV4 per ACIP recommendations for the 2022-2023 season. Persons aged ≥ 65 years will receive high-dose IIV4 (HD-IIV4) or saline placebo injection. Participants will receive the vaccines in an observer-blinded manner on the same day as they receive mRNA COVID-19 vaccine. Seven to fourteen days later (Visit 2) those who received IIV4 at Visit 1 will receive placebo and those who received placebo on at Visit 1 will receive IIV4 (SD-IIV4 or HD-IIV4, depending upon age). Participants will then receive a second mRNA COVID-19 vaccine (Visit 3), if applicable, and according to the recommended schedule for vaccination for the respective mRNA COVID-19 vaccine product used.

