### Major Protocol Violations for Influenza and SARS-CoV-2 Immunogenicity Analysis

1. Major Protocol Violations for Exclusion from Immunogenicity Populations:
  - a. Not all study vaccines received
  - b. No pre- and/or post-vaccination blood draw or insufficient volume for assay analysis for respective vaccine\*
  - c. Receipt of any other vaccine between the pre- and post-vaccination blood draws
  - d. New immunosuppression disorders between the pre- and post-vaccination blood draws or receipt of immunosuppressive medication between the pre- and post-vaccination blood draws
  - e. Subject who was inadvertently enrolled and randomized to the study, though they were later learned to have had met the following criteria (see f-k below) for study exclusion that would have affected immunogenicity
  - f. Influenza vaccine receipt during the current influenza season prior to study enrollment
  - g. COVID-19 vaccine prior to enrollment unless presenting for a booster dose
  - h. Prior receipt of non-mRNA COVID-19 vaccine
  - i. Use of oral or parenteral corticosteroids ( $\geq 20\text{mg/day}$  prednisone equivalent) or high-dose inhaled glucocorticoid for  $\geq 14$  consecutive days within the preceding 30 days
  - j. Has an active neoplastic disease (excluding non-melanoma skin cancer), a history of any hematologic malignancy
  - k. Has a history of receiving immunoglobulin or other blood product (with exception of Rh immunoglobulin) within the 3 months prior to study vaccination or during the study including Evushield or other COVID-19 monoclonal antibody.
  - l. Subject who was enrolled for both the 2021-22 and 2022-23 flu seasons may be included in immunogenicity for the 2021-2022 season only.

\*Blood draws will not be considered out of window as long as blood was collected within -7/+14 days of the protocol window for the respective vaccine

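### The forward bar on other vaccines in exclusion criterion 8 is tied to a second mRNA dose, which gives booster participants no usable end date and leaves the primary diary windows unprotected for them

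*Protocol*

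**What the plan says.** Criterion 8 of Protocol 4.2 has two parts.

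- The look-back runs from enrolment and works for everyone. It starts with "Receipt of any licensed inactivated vaccine within 2 weeks prior to enrollment in this study" and sets 4 weeks for live vaccines and 6 weeks for two named adjuvanted vaccines.
- The forward part excludes anyone "planning receipt of any vaccines following enrollment until 6 weeks after receipt of the second dose of mRNA COVID-19 vaccine". It has no separate wording for booster participants.

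The Protocol Summary states: "Participants receiving a booster dose of mRNA COVID-19 vaccine will receive a single COVID-19 dose within the study". Section 1.1 notes that "recommendations for the interval between the primary series and booster dose have also been shortened to 5 months". Section 1.2 says "it is expected that most adults and many children receiving an mRNA COVID-19 vaccine in this study will be receiving a booster dose".

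The primary endpoint counts moderate or worse fever, chills, myalgia or arthralgia on Days 1-7 after Visit 1 and after Visit 2. Under Protocol 5.4.1, solicited symptoms are all taken to be vaccine-related and receive no causality assessment.

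The only analysis rule on non-study vaccines is SAP Appendix 1, item c: "Receipt of any other vaccine between the pre- and post-vaccination blood draws". It removes participants from the immunogenicity analysis. Full Analysis Population 1 (Protocol 7.1.2, SAP 6.1), which carries the primary endpoint, has no such rule. The one sensitivity analysis in SAP 9 concerns IIV4 and placebo given in the wrong order.

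**The concern.** An eligibility rule that works for the two-dose stratum has no workable meaning in the booster stratum. If second dose means the second dose of the primary series, the bar expired before the participant enrolled. If it means a second dose in the study, that dose never comes and the bar has no end. Three sites could apply it in different ways.

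On the literal reading the two halves of the criterion also sit oddly together. One of the named adjuvanted vaccines given five weeks before Visit 1 excludes a booster candidate. The same vaccine planned for two days after Visit 1, inside the diary window, does not.

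A reaction to a non-study vaccine in a diary window would be scored as a primary event. Events unrelated to assignment raise the rate in both groups, which costs power. They also shrink a true difference, which in a noninferiority safety trial favours the conclusion being sought.

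**Working it through.** **1. Does the bar reach the diary windows?**

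- Shortest stated interval from primary series to booster: 5 months, about 150 days (Protocol 1.1).
- End of bar, literal reading: 150 − 42 = 108 days before Visit 1.
- Latest Visit 2: 14 + 2 = 16 days after Visit 1, i.e. study day 17 (Protocol Table 7). Its diary covers days 0-6 after that visit, so it ends by study day 17 + 6 = 23.
- Overlap of bar and diary windows for booster participants: none. To reach study day 23 (22 days after Visit 1), the second dose would have to lie within 42 − 22 = 20 days before Visit 1.

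**2. Does other text close the gap?**

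- Temporary delay (Protocol 4.3) covers recent febrile illness only.
- The booster schedule (Table 7) asks specifically about additional COVID-19 vaccinations, at the last phone visit. Concomitant medications are collected, but nothing says that this includes other vaccines.
- SAP Appendix 1, item c, acts on immunogenicity only.

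**3. The plan's own power figure**

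Inputs (Protocol 7.1.1): 15% in the Sequential group, margin 10 points, one-sided alpha 0.025, 214 per group. Equal true rates are assumed.

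- SE = √(2 × 0.15 × 0.85 / 214) = 0.0345
- Power = Φ(0.10/0.0345 − 1.96) = 82.56%, against 82.6% stated. The figure reproduces.

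**4. Illustrative effect of non-study vaccines**

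None of these three inputs is in the documents; they are assumptions.

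- *b*, booster share of the trial: 50-90%
- *u*, booster participants receiving another vaccine in a diary window: 2-20%
- *q*, chance that it causes a qualifying event: 15-30%

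The effect is taken as independent and equal in both groups. The added event chance over the whole group is *x = b·u·q*.

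- Event rate under no difference: p′ = 0.15 + 0.85x. Power = Φ(0.10/√(2p′(1−p′)/214) − 1.96).
- Null boundary, 15% against 25%: the 10-point excess becomes 0.10(1 − x). Type I error = Φ((0.10 − 0.10(1−x))/SE − 1.96), with SE taken from the two shifted rates.

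| b | u | q | x | p′ | Power | 10-point excess becomes | Type I error |
|---|---|---|---|---|---|---|---|
| 50% | 2% | 15% | 0.0015 | 15.1% | 82.3% | 9.98 | 0.025 |
| 50% | 5% | 30% | 0.0075 | 15.6% | 81.3% | 9.93 | 0.026 |
| 90% | 5% | 30% | 0.0135 | 16.1% | 80.3% | 9.87 | 0.027 |
| 90% | 10% | 30% | 0.0270 | 17.3% | 78.1% | 9.73 | 0.029 |
| 90% | 20% | 30% | 0.0540 | 19.6% | 74.1% | 9.46 | 0.034 |

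The third row is the least favourable case with uptake of 5% or less. The last row is the least favourable case examined.

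**The case against.** The strongest reply is that this is an ambiguity of wording with a small effect. Much of that stands.

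- **Site practice.** A reader might infer that sites treated the bar as expired and that booster participants did receive other vaccines. No text shows this. A site could equally read the bar as open-ended, or use the investigator's discretion under criterion 21. Criterion 8 also screens plans at enrolment; it does not prohibit vaccines during the study for anyone.
- **Share of the trial.** It is tempting to say that most of the trial is affected. Section 1.2 speaks of most adults and many children, and no booster share or age mix is given.
- **Bias between groups.** Assignment is randomized and participants are blinded, so receipt of other vaccines should not depend on group. The issue is noise and dilution; the documents give no ground for a differential bias.
- **Size.** Uptake and event chance have no source in the documents. At low uptake the effect is slight.
- **Prior influenza vaccine.** Criterion 2 names only "Prior receipt of IIV4 during the respective influenza season in which they are being enrolled", and a reader might conclude that someone given a recombinant influenza vaccine earlier in the season is eligible. Section 3.1 limits enrolment to people "who have not received their influenza vaccine during the influenza season during which they are recruited", and inclusion criterion 3 requires an intention to receive influenza vaccine under the guidelines. This mismatch is editorial.

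What the reply does not supply is a working end date for booster participants, or any handling of non-study vaccines in the primary analysis.

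**Conclusion.** The point holds as a defect in a stated rule, with modest consequences. For booster participants the forward bar in criterion 8 is either void or endless. On the literal reading it leaves both primary diary windows open to planned non-study vaccines, and the primary analysis has no provision for them.

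No stated figure in the plan is wrong, and the sample-size arithmetic reproduces. With assumed uptake of 5% or less among booster participants, a booster share up to 90% and an event chance up to 30%, power falls by at most about 2.3 points (82.6% to 80.3%) and type I error rises to about 0.027. Only at much higher assumed uptake, such as 20%, does power drop to about 74% and type I error reach 0.034. The change is worth making because it is cheap, planned power is little above 80%, and the dilution runs towards noninferiority.

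**What to change.** 1. Reconcile criterion 8 with the single-dose booster schedule. Anchor the forward bar to a study visit that booster participants have, so that it covers at least both primary diary windows. The sponsor should set its length.
2. Record the dates of all non-study vaccines during follow-up. Applying SAP Appendix 1, item c, already presupposes much of this information, but the schedules name only COVID-19 vaccinations.
3. Add to SAP 9 a sensitivity analysis of the primary endpoint that excludes or flags participants who received a non-study vaccine inside a diary window, with counts by group to show whether receipt was balanced. For people already enrolled, this is the part that still helps, provided the dates can be obtained.
4. In the same edit, align the influenza vaccine wording of criterion 2 with Section 3.1.

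Cost: a short protocol clarification, one added data item and one extra analysis. A few booster candidates with another vaccination planned would be deferred or not enrolled.
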